### **Disease control rate**

DCR is defined as the proportion of participants with BOR of CR, PR, or stable disease (SD) per RECIST 1.1.

DCR will be estimated by treatment group and for the Phase II part by T790M status in Group 1 and by sub-group otherwise together with the exact binomial 95% CI (Clopper and Pearson 1934).

### **Time to response**

TTR is defined as the time between the date of start of treatment and the date of first documented response (CR or PR, which must be confirmed subsequently). For participants who did not achieve a confirmed PR or CR, the TTR will be censored at the last adequate tumor assessment date.

TTR will be described using the Kaplan-Meier method including the estimated median (in months) with 95% CI, as well as the 25th and 75th percentiles. For the Phase Ib part the summary will be provided only in treatment groups with sufficient numbers of participants. Summary statistics of TTR for participants whose best response is CR or PR will also be provided.

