#### **10.7.2 Efficacy objectives**

CT/MRI assessments will be used for all efficacy assessments of anti-tumor activity on study. BOR, ORR, PFS, DCR, duration of response (DOR) and Time To Response (TTR) will be defined as per RECIST 1.1 (see [Section 14.1](#)) based on investigator assessment. The analyses will be based on the FAS for groups 1 to 4 and the EAS for Group 5. Summaries by group will be based on baseline mutation status and prior systemic antineoplastic therapies as specified in the eCRF. Listings of efficacy endpoints will be presented by treatment group.

If available, the results of the central evaluations by BIRC may be used for secondary analyses purposes.

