#### 14.1.3.2.7 Time to response

**Time to overall response (CR or PR)** is the time between date of randomization/start of treatment until first documented response (CR or PR). The response may need to be confirmed depending on the type of study and its importance. Where the response needs to be confirmed then time to response is the time to the first CR or PR observed.

Although an analysis on the full population is preferred a descriptive analysis may be performed on the “responders” subset only, in which case the results should be interpreted with caution and in the context of the overall response rates, since the same kind of selection bias may be introduced as described for duration of response in [Section 14.1.3.2.6](#). It is recommended that an analysis of all patients (both responders and non-responders) be performed whether or not a “responders only” descriptive analysis is presented. Where an inferential statistical comparison is required, then all patients should definitely be included in the analysis to ensure the statistical test is valid. For analysis including all patients, patients who did not achieve a response (which may have to be a confirmed response) will be censored using one of the following options.

- at maximum follow-up (i.e. FPFV to LPLV used for the analysis) for patients who had a PFS event (i.e. progressed or died due to any cause). In this case the PFS event is the worst possible outcome as it means the patient cannot subsequently respond. Since the statistical analysis usually makes use of the ranking of times to response it is sufficient to assign the worst possible censoring time which could be observed in the study which is equal to the maximum follow-up time (i.e. time from FPFV to LPLV)
- at last adequate tumor assessment date otherwise. In this case patients have not yet progressed so they theoretically still have a chance of responding

**Time to overall complete response (CR)** is the time between dates of randomization/start of treatment until first documented CR. Similar analysis considerations including (if appropriate) censoring rules apply for this endpoint described for the time to overall response endpoint.

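### Time to response censors non-responders who have progressed or died at their last adequate scan, which biases the all-participant Kaplan-Meier median and quartiles towards response

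*Protocol*

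**What the plan says.** Section 10.7.2.1 (Time to response) plans an all-participant summary: "TTR will be described using the Kaplan-Meier method including the estimated median (in months) with 95% CI", plus the 25th and 75th percentiles. For participants without a confirmed response it gives a single rule: "For participants who did not achieve a confirmed PR or CR, the TTR will be censored at the last adequate tumor assessment date". It makes no exception for progression or death. A second, restricted summary is also planned: "Summary statistics of TTR for participants whose best response is CR or PR will also be provided".

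Section 10.7.2 points to Appendix 1 for the definitions, saying that "duration of response (DOR) and Time To Response (TTR) will be defined as per RECIST 1.1", with a reference to Section 14.1. In Section 14.1.3.2.7 the analysis of all patients is introduced by "patients who did not achieve a response (which may have to be a confirmed response) will be censored using one of the following options". Two cases follow:

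- Censoring "at maximum follow-up (i.e. FPFV to LPLV used for the analysis) for patients who had a PFS event", meaning progression or death from any cause. The reason given is "In this case the PFS event is the worst possible outcome as it means the patient cannot subsequently respond".
- Otherwise, censoring at the last adequate tumor assessment. The reason given is "In this case patients have not yet progressed so they theoretically still have a chance of responding".

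**The concern.** Kaplan-Meier treats a censored participant as having the same future chance of the event as those still at risk. For TTR the event is a response, and a participant who has progressed or died has no such chance. Section 14.1.3.1 excludes assessments after progression from best overall response, and Section 10.5.3 counts these participants as progressive disease. Progression and death are therefore competing events. Removing those participants from the risk set at an early scan shrinks the denominator at every later response time.

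The definitions in Appendix 1 make this worse. Under Section 14.1.3.2.8 the last adequate assessment must be a complete response, partial response or stable disease, so the progression scan does not count. A participant who progresses at the first scan has no adequate post-baseline assessment and is censored at treatment start, with a duration of 1 day (Section 14.1.4.5.1). The earliest failures thus drop out before any response is counted.

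At stake are the median and quartiles of a named secondary endpoint for Phase Ib and Phase II Groups 1 to 4.

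**Working it through.** The protocol states no TTR figure, so there is none to reproduce. The check applies both censoring rules to the same data.

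**Inputs from the protocol.** First post-baseline scan at the start of Cycle 3 (week 8), then 8-weekly (Section 7.2.1). Group 3: 22 responses in 40 (Section 10.5.2.2). Group 1 subgroup: 5 responses in 20 (Section 10.10). Censoring dates as above.

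**Assumed, not in the protocol.** When responses and progressions occur, and a maximum follow-up of 104 weeks.

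**Direction.** Cumulative response is 1 − Π(1 − d/n), where d is the number of first responses and n the number at risk at each response time. Both rules use the same d. The appendix rule never has a smaller n, because progressed non-responders stay at risk to the end. Hence 1 − S as written is at least as high at every time, and each quantile is at least as early.

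**Worked example, 22/40.** First responses: 14, 5 and 3 at weeks 8, 16 and 24. Non-responders: 4 progress at the first scan (censored day 1); 5, 4 and 3 progress with last adequate scans at weeks 8, 16 and 24; 2 are ongoing at week 32.

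| Week | As written: d/n | 1 − S | Appendix 1: cumulative |
|---|---|---|---|
| 8 | 14/36 | 0.389 | 14/40 = 0.350 |
| 16 | 5/17 | 0.569 | 19/40 = 0.475 |
| 24 | 3/8 | 0.730 | 22/40 = 0.550 |

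The median is 16 weeks as written and 24 weeks under the appendix rule. The first quartile is 8 weeks under both.

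**Worked example, 5/20.** First responses: 3, 1 and 1 at the same weeks. Non-responders: 5 progress at the first scan; 4, 3 and 2 progress with last adequate scans at weeks 8, 16 and 24; 1 is ongoing at week 32. As written, d/n is 3/15, 1/8 and 1/4, giving 1 − (0.8 × 0.875 × 0.75) = 0.475. The appendix rule gives 5/20 = 0.25. The first quartile moves from week 24 to week 16.

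**Worked example, 8/20 (an assumed count).** First responses: 5, 2 and 1. Non-responders: 4 progress at the first scan; 4, 2 and 1 progress later; 1 is ongoing. As written, d/n is 5/16, 2/7 and 1/3, giving 0.31, 0.51 and 0.67, so a median of 16 weeks is reported. Under the appendix rule the curve stops at 0.40 and the median is not reached.

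**Simulation.** Responders respond at scans 1, 2 and 3 in proportions 70/20/10%. The median progression-free survival (PFS) of non-responders is varied.

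| Non-responder median PFS | n=40, true 0.55: implied response as written | n=20, true 0.25: implied response as written | n=20: finite median reported |
|---|---|---|---|
| 2 months | 0.83 | 0.51 | about 49% |
| 4 months | 0.69 | 0.36 | 16% |
| 6 months | 0.64 | 0.32 | 8% |
| 12 months | 0.59 to 0.60 | 0.28 | 3% |

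Under the appendix rule the implied response equals the true rate, and a finite median at n=20 appears in 1 to 2% of trials. For n=40 and a true rate of 0.55, the two medians are identical in about 26% of trials at 2 months, rising to about 80% at 12 months. The first quartile is identical in at least 97%.

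A second set used slower responses and a progression hazard of 0.15 to 0.50 per scan. For n=40 and a true rate of 0.55 it gave 0.63 to 0.87, with a typical median of 16 weeks as written against 24. For n=40 and a true rate of 0.40, a finite median appeared in 39% to 98% of trials against about 14%.

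**The case against.** The strongest case on the other side has four parts.

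1. **The appendix may not bind.** It is a generic guideline, its lead-in speaks of options, and Section 14.1.4.1 leaves study-specific decisions to the protocol or SAP. It justifies the maximum follow-up date partly through the ranking of response times, and it insists on including all patients only for inferential comparisons. A reader might infer that Section 10.7.2.1 breaks a binding rule. The text does not support that. It is an unexplained departure from guidance that the protocol itself cites. Even so, the two bullets are complementary cases, and the reason for using the last assessment date applies only to patients who have not progressed. A free choice between them would not make the estimator valid for the others.

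2. **The median may not move.** A reader might infer that the reported median is always too short. It is not: on an 8-weekly grid the two rules often give the same median, and nearly always the same first quartile at n=40 with a true rate of 0.55. This limit stands.

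3. **The inflated cumulative response is not a planned output.** A reader might expect a published curve overshooting the response rate. Section 10.7.2.1 plans plots for duration of response, PFS and overall survival, but no plot or cumulative rate for TTR. The figures of 0.83 to 0.60 measure the mechanism. What would be reported are the median and quartiles derived from it.

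4. **Little depends on TTR.** No hypothesis, decision rule, interim analysis or sample size uses it. It is not a Group 5 endpoint (Section 10.7.2.2), Group 2 has about five participants, and Phase Ib is summarised only where numbers suffice. The responders-only summary does not have this bias. This is accepted, and it keeps the point modest.

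**Conclusion.** The censoring rule is wrong as written for participants who have progressed or died, and it departs without explanation from Section 14.1.3.2.7. The all-participant TTR estimate is biased towards earlier and more frequent response. Its median and quartiles are never later than under the appendix rule, can be too early, and can be finite where they should be not reached.

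The direction follows from the risk sets and needs no assumption. The size does: it rests on PFS in non-responders and on when responses occur, neither of which the protocol gives. Across an assumed median of 2 to 12 months the effect ranges from substantial to small. It is greatest where non-responders progress early, and a spuriously finite median is possible where the response rate is below 50%.

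The effect is confined to one descriptive secondary summary in Phase Ib and Groups 1 to 4. A reader might carry the bias over to the primary overall response rate. The documents do not support that, because the response rate is analysed separately as a proportion and does not use this censoring rule.

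**What to change.** In Section 10.7.2.1, replace the censoring sentence with the two-case rule of Section 14.1.3.2.7:

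- Participants without a confirmed response who have a PFS event (progression or death from any cause) are censored at the maximum follow-up time used for the analysis (FPFV to LPLV).
- All other participants without a confirmed response are censored at their last adequate tumor assessment.

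An equivalent remedy is a cumulative incidence function for response with progression or death as the competing event. Keep the responders-only summary.

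The cost is one sentence and a line of programming, with nothing further to collect. The drawback is that the all-participant median may then be not reached, particularly where fewer than half the participants respond. That is the correct result in such a group, and the responders-only summary still describes how quickly responses occurred.

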### **Progression-free survival**

PFS is defined as the time from the date of first dose of study treatment to the date of first documented disease progression per RECIST 1.1 or death due to any cause. If a participant did not have an event or received any further anticancer therapy before documented disease progression, PFS will be censored at the time of the last adequate tumor assessment. By default, if disease progression or death is documented after one single missing tumor evaluation, the actual event date of disease progression/death will be used for the PFS event date. If disease progression or death is documented after two or more missing tumor evaluations, the PFS time of these participants will be censored at the date of the last adequate tumor assessment without PD. Clinical deterioration without objective radiological evidence will not be considered as documented disease progression.

PFS will be described using the Kaplan-Meier method including the estimated median (in months) with 95% CI, 25th and 75th percentiles. For the Phase Ib part the summary will be

provided only in treatment groups with sufficient numbers of participants. For the Phase II part a Kaplan Meier plot will also be presented. In addition, the PFS rates and 95% confidence intervals at 6, 12, 18 and 24 months will be estimated.

### **Overall survival**

OS is defined as the time from the date of first dose of study treatment to the date of death due to any cause. Overall survival time for participants who are alive at the analysis cut-off date, who withdrew consent, or are lost to follow-up will be censored at the date of last contact prior to the cut-off date.

OS will be described using the Kaplan-Meier method including the estimated median (in months) with 95% CI, 25th and 75th percentiles, as well as the corresponding plot. The summary will be provided only in treatment groups with sufficient numbers of participants.

#### **10.7.2.2 Secondary efficacy endpoints for Phase II Group 5**

DOR, DCR, and PFS for capmatinib monotherapy will be analyzed as secondary efficacy endpoints for Group 5.

The analyses will be based on the EAS. The endpoint definition follows the description in Section 10.6.2.1.

#### **10.7.3 Pharmacokinetics**

The PAS will be used in all concentration pharmacokinetic data analysis and PK concentration summary statistics. The FPAS will be used for all PK parameters summary statistics.

For each of the three analytes capmatinib, nazartinib and LMI258, concentration data will be listed and summarized by Cycle, Study Day, time point, and treatment group (i.e. each dose combination of capmatinib and nazartinib in the Phase Ib part and Group 1, 2, 3 or 4 in the Phase II part, respectively). Descriptive statistics will include arithmetic and geometric mean, median, standard deviation, coefficient of variation (CV%), geometric mean CV%, minimum and maximum. Zero concentrations will not be included in the geometric mean calculation. Individual concentration-time profile as well as mean concentration-time profile will be plotted.

PK parameters will be determined for all PK-evaluable participants with non-compartmental method(s) using Phoenix WinNonlin version 6.2 or above (Pharsight, Mountain View, CA).

Derived PK parameters, such as those listed in Table 10-1, will be summarized with descriptive statistics, including arithmetic and geometric means, median, standard deviation, CV%, geometric mean CV%, minimum and maximum. Only median values and ranges will be given for Tmax. Missing data will not be imputed.

To estimate the effect of food on the PK of capmatinib and nazartinib when given in combination with food after a single dose at steady state, the PK data on Cycle 1 Day 1 and on Cycle 2 Day 1 from Phase II Group 4 will be compared to the PK data with fasted condition from Phase Ib, and other Groups of Phase II.

The primary PK parameters (AUC0-t and Cmax) on Cycle 1 Day 1 and on Cycle 2 Day 1 respectively, will be log-transformed and analyzed with an ANOVA model including food

status (fed or fasted) as fixed effect. The model-based, between-treatment mean differences and corresponding two-sided 90% confidence intervals (CIs) will be calculated on the log-scale. The between-treatment differences and 90% CIs will then be back transformed to the original scale to obtain the geometric mean ratios and corresponding 90% CIs. For Tmax, median and range of difference between treatment groups will be provided.

**Table 10-1 Noncompartmental pharmacokinetic parameters**

AUClast	The AUC from time zero to the last measurable concentration sampling time (tlast) (h*ng/ml  )
AUC0-t	The AUC from time zero to t hours after administration (h*ng/ml)
AUCtau	The AUC calculated to the end of a dosing interval (tau) (h*ng/ml)
Cmax	The maximum (peak) observed plasma drug concentration after single dose administration (ng/ml)
Tmax	The time to reach maximum (peak) plasma drug concentration after single dose administration (h)
Lambda_z	Smallest (slowest) disposition (hybrid) rate constant (time  ) may also be used for terminal elimination rate constant (time  )
T1/2	The elimination half-life associated with the terminal slope (λz) of a semi logarithmic concentration-time curve (h). Use qualifier for other half-lives
CL/F	The total body clearance of drug from the plasma (L/h)
Vz/F	The apparent volume of distribution during terminal phase (associated with λz) (L)
Racc	The accumulation ratio, calculated as AUCtau/AUCtau(C1D1)

### 10.7.3.1 Data handling principles

Missing concentration values will be reported as is in data listings. Concentration values of capmatinib, nazartinib, and LMI258 below the respective Lower Limit of Quantitation (LLOQ, BLLOQ) will be handled as zero in summary statistics, and reported as is in data listings. Any missing pharmacokinetic parameter data will not be imputed.

## 10.9 Interim analysis

### Phase Ib part

No formal interim analyses are planned. However, the dose-escalation design foresees that decisions based on the current data are taken before the end of the study. More precisely, after each cohort in the dose-escalation part, the next dose will be chosen depending on the observed

data. Details of this procedure and the process for communication with investigators are provided in [Section 6.2.3](#).

## Phase II part

A futility interim analysis (IA) will be conducted for Group 3 (EGFRmut, T790M negative, any MET, 1L antineoplastic) and Group 5 (EGFRmut, T790M-, MET GCN  $\geq$  5, 2L, EGFR TKI resistant). No interim analysis is planned for Groups 1, 2 and 4. However, individual participant data will be reviewed on an ongoing basis by the study team across the duration of the trial ([Section 8.5](#)).

### Group 3 (EGFRmut, T790M negative, any MET, 1L antineoplastic)

One interim analysis for futility will be performed for participants enrolled in Group 3 (participants in first line setting) when approximately 20 participants have completed at least 4 cycles of treatment or discontinued treatment prior that time. A close monitoring of the first 20 measurable participants will be performed. All evaluable participants at the time of the data cut-off for the interim analysis will be used.

The decision whether to continue or stop enrollment and/or treatment will be based on the probability of success (PoS). PoS is the probability to have a positive conclusion at the end of the study, given the interim data. Denoting the number of participants at interim by  $n_1$  and the number of responders at interim by  $r_1$ , PoS is found as

- $PoS = \text{Prob} [\text{at least } x-r_1 \text{ responders in } 40-n_1 \text{ participants} \mid r_1 \text{ responders in } n_1 \text{ participants}]$

The number of responders ( $x-r_1$ ) to be observed in the remaining  $40-n_1$  participants follows a Beta-binomial distribution. This is used in order to calculate PoS.

The enrollment and/or treatment may be stopped at the interim analysis if  $PoS < 0.10$ , i.e., if less than 9 out of the first 20 participants have the best response of CR or PR. The criterion (number of responders) will be based on the actual number of participants in the FAS at the time of the interim analysis.

If futility is concluded, the enrollment of 1L participants (Group 3 and 1L participants in Group 4) may be stopped. The enrollment in opened groups with pre-treated participants will continue.

[Table 10-2](#) provides the probabilities of success at the primary analysis based on different numbers of responders observed at the interim analysis. For 9 or more responders PoS exceeds 0.10 and the study will continue at interim.

**Table 10-2 Probability of success at the primary analysis based on various numbers of responders observed at the IA for Group 3**

Responders at IA out of 20 evaluable participants at IA	Probability of Success
8/20	0.04
9/20	0.14
10/20	0.33
11/20	0.57
12/20	0.79

